Within Ohio, 50 of the total 88 counties (56.8%) are considered rural according to Rural-Urban Continuum Codes (RUCC). These counties have a population of about 2.3 million, most of whom are Caucasian. Our study will target adults 20-64 years old who reside in rural Ohio counties. We will enroll up to 50 adults 20-64 years of age in the designated counties.

C.3.b Eligibility Criteria

Inclusion Criteria: 1) $BMI \geq 25\text{kg}/\text{m}^2$; 2) Age ≥ 20 years and <65 years; 3) Not currently participating in any weight loss intervention or meeting the 2018 Physical Activity Guidelines for Americans (150 min/week of moderate-intensity exercise or 75 min/week of vigorous exercise); 4) Ability to walk two city blocks (about 400 steps) comfortably; and 5) Ability to speak and read English.

Exclusion Criteria: 1) Prior cancer diagnosis (except non-melanoma skin cancer) or severe medical conditions such as unstable cardiovascular disease or digestive disorders that would preclude physical activity and dietary intervention; 2) pregnant or nursing women (if one becomes pregnant over the course of the study, she will be asked to report to research staff); and 3) unable to give informed consent.

Potential participants will be screened for eligibility by phone or online survey. To determine whether an interested individual should consult with his or her physician before beginning an exercise program, potential participants who self-reported to have pre-existing health conditions (e.g., heart problems, insulin-dependent diabetes, poorly controlled blood pressure, other severe disease) will be asked to obtain medical clearance before enrollment. For potential participants who self-reported any health condition that may preclude them from the exercise/dietary modification (e.g., poorly controlled blood pressure, insulin-dependent diabetes, any heart disease, or any other severe disease), we will ask their permission to contact to their physicians to obtain medical clearance. Their physicians must fax, email or mail a medical clearance form (see 10. Medical Clearance Form) to OSU by baseline assessment so that the individual can participate in the study. If physicians indicated the participant is not eligible for our study, we will contact the participants by phone/email to inform their ineligibility (see 1d. Not eligible from physician clearance).

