The consent process will be documented in detail including any questions asked by the individuals and the responses provided by research staff. The research staff will date and sign the documentation. In addition, the time the consent process began and ended will also be documented. Prior to the beginning the baseline assessment, participants will be asked once again if they understand the requirements of the study and if they wish to continue. Any subsequent changes to the informed consent process will be submitted to the OSU IRB for approval prior to activation.

Participants assigned to the weight loss group will notify the research study staff of any pre-existing medical conditions, including injuries and recent surgeries, at baseline before they start the weight loss intervention and will inform the research study staff should they experience any medical problems, including injuries, over the course of the weight loss program. Their responses at baseline and throughout the weight loss intervention will be recorded on an Adverse Events Log.

Table 2. Dietary intake and exercise goal.

Dietary budget per day		
Baseline Weight	< 250 lbs	≥250 lbs
Calorie (kcal)	1200-1500	1500-1800
Fat (g)	40-50	50-60
Protein (g)	60-75	75-90
Aerobic exercise (moderate-intensity) per week		
Goal	150-200 min	
Week 1	30-60 min	
Week 2-4	↑ 30 min till reach 150 min	
Week 5-15	>150 min/week	

C.4 Weight Loss Intervention

C.4.a Overview

The proposed weight loss intervention is a 15-week telephone-based, multi-component approach adapted from the Healthy Living and Eating Program (73), which was designed for cancer patients. We will modify the program from the in-person group sessions to a remotely accessible telephone-based intervention to reduce the burden of travel for rural populations and transform the program from a cancer patient's focus to one of a general population with obesity. Participants randomized

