The objective of the behavioral component is to promote increased self-efficacy and social support for lifestyle modifications and gradually facilitate participants' transition toward successful independent self-regulation of a healthy diet and physical activity. The behavioral component focuses upon the acquisition and practice of self-regulatory skills in conjunction with a continuous problem-solving model of behavior change to empower participants to exert greater control over their behavior, cognition, and environment. The behavioral component is designed to: a) increase health knowledge of the benefits of physical activity and dietary modifications; b) enhance self-efficacy and positive outcome expectancies through the promotion of a series of successful experiences in changing exercise and eating behavior; and c) improving self-regulation of exercise and eating behaviors through the use of goal-setting, self-monitoring, stimulus control, cognitive restructuring, and barrier problem-solving strategies. The efficacy of this approach for promoting adoption and maintenance of exercise and dietary behavior change has been demonstrated in prior randomized controlled trials that [name] has served as principal and co-investigator on other studies (106-109).

C.5 Active Control Group

At the beginning of the study, participants randomized to the active control arm will receive education brochures (will be submitted in the first amendment) describing the American Institute for Cancer Research physical activity and dietary guidelines. Participants will be asked to meet the 2018 Physical Activity Guidelines for Americans (150 min/week of moderate-intensity exercise or 75 min/week of vigorous exercise), and increase fruit and vegetable intake, reduce fat intake, reduce sugary drink, increase consumption of whole grain, and increase water intake. An exercise manual with access Online YouTube videos (as another option) will be available as examples for proper exercise form for strength training. We will also encourage them to self-monitor weight, dietary intake, and physical activity through MyFitnessPal or paper log. To achieve the retention and provide motivation and strategies for behavioral change in the active control group, participants will receive a Fitbit and the lifestyle modification manual at the end of the study.

C.6 Covid-19 Safety Protocols and Planning

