We considered using a standard measure of body composition using Dual-energy X-ray absorptiometry (DXA) but opted not to as this is likely to add the burden of travel to facilities equipped with DXA. However, we will assess body composition using a 3-D Styku body scanner, which is portable to rural community-settings and can provide valid and reliable data on body composition. Together with using Cholestech LDX to evaluate participants' lipid profiles, the proposed study is innovative to test new point-of-care approaches to assess disease risk factors in rural populations.

D DATA HANDLING AND ANALYSES

D.1. Outcome Analysis Plan

D.1.a Primary outcome

The feasibility of completing the study is defined as the percentage of enrolled participants who complete the study. If we observe an 80% completion rate in the weight loss intervention group (n=30), the 85%, 90%, and 95% confidence intervals (CIs) for the completion rate would be (69.5, 90.5), (68.0, 92.0), and (65.7, 94.3), respectively. If the true completion rate is 80%, we have 95% power to rule out the unacceptable 50% completion rate with 95% confidence (one-sided).

The acceptability of the weight loss intervention is the percentage of participants in the weight loss intervention group who engage at least 75% of the weekly telephone counseling session. Intervention-related adverse events, satisfactory, and other feasibility assessments, such as the percent of initial contact to enrollment, reasons for consent refusal, barriers to adherence to weekly goals, and reasons for drop-out will also be assessed.

D.1.b Secondary outcome

Significance test for the preliminary efficacy of the lifestyle intervention will quantify the difference in means using repeated measures analysis of variance (ANCOVA) statistical model to adjust baseline values and control for the effect of age. The sample size of 30 participants in the weight loss group and at least 15 in the active control group is feasible to recruit for a pilot/preliminary efficacy study that accounts for a projected attrition rate of 20% yet also still provides adequate power to detect meaningful, moderate to large effect size (0.54-0.72) on weight loss, body composition, inflammatory markers, and lipid profiles.

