also a risk of muscle injury, which may require medical attention, may take several months to heal, and may limit activities of daily living for a period of days, weeks, or months. Participants will be informed that there is an increased risk with starting a physical activity program and be advised of all of the potential risks. Additionally, [name] and research staff with training in exercise physiology and behavioral changes will be directly involved in conducting physical fitness tests and delivering exercise components.

There is a slight risk of breach of confidentiality, but steps are in place to protect participants' personal information. Electronic data will be stored behind a firewall and accessed only by study staff through password-protected computers. Paper-based data will be stored in a locked cabinet within a locked file room.

Collectively, the participants will be assuming no more than minimal risk in completing the assessment protocol and the minimal risk inherent to completing the assessments will be mitigated via stringent pre-test medical screening and during testing supervision.

E.2 Benefits of participation

Participants may gain awareness of healthy eating and physical activity from evidence-based program. Participants in the telephone-based counseling group will receive a physical activity tracker (e.g., Fitbit) at the beginning of the study, and weekly telephone-based weight loss counselling for 15 weeks. Participants in the active control group will also receive a physical activity tracker and lifestyle modification manual at the end of the study. All participants will receive regular body weight, body composition, and blood tests for lipid profiles and inflammatory biomarkers free of charge.

E.3 Adverse events

Adverse events, including any unfavorable and unintended sign (e.g., abnormal laboratory finding or symptom) will be collected as they occur, regardless of whether it is considered related to the weight loss intervention. Musculoskeletal injuries and previously undocumented major medical events incurred during the intervention will be systematically collected on all participants during the study period using standardized forms from our prior work. Patients will have instructions to contact the PI or their primary health providers to discuss and manage any possible side effects. The PI, study coordinator should immediately be contacted in the event such a problem arises.

E.3.a Severity

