The adverse event form will be used by study staff to report injuries or other adverse events reported by participants throughout the study. The patient will be observed and monitored carefully until the condition resolves, stabilizes, or its cause is identified. All adverse events, including laboratory abnormalities, will be followed up according to good medical practices. Information to be recorded includes: 1) specific type of reaction; 2) duration of reaction; 3) severity/grade of reaction according to the NCI Common Terminology Criteria for Adverse Events v4.0 (CTCAE); 4) suspected cause of the reaction (i.e. possibly or probably related to one of the following: study treatment, progression of disease, concurrent medications, concurrent illness, or other factors); 5) changes made in the administration of the study intervention and other actions taken to alleviate the clinical event; and 6) patient's response to medical interventions.

E.3.d Reporting

In accordance with IRB guidelines, serious adverse events will be reported within 10 days of the investigator's or research staff members' learning of the event to OSU IRB. OSU IRB Event Reports should be submitted through BuckIRB at: <http://orpp.osu.edu/irb/buck-IRB/>. Events resulting in temporary or permanent interruption of study activities by the investigator or sponsor to avoid potential harm to subjects should be reported within 48 hours whenever possible.

All events that may represent unanticipated problems involving risks to subjects or others will be promptly reported (as described above), regardless of whether they occur during or after the study, or involve a subject who has withdrawn from or completed study participation. If changes to the research or consent process are proposed as a result of the event, or if additional information will be provided to current and/or past participants, a protocol amendment will be submitted for IRB review.

Related events involving risk but not meeting the prompt reporting requirements will be reported to the IRB in summary form at the time of continuing review.

E.4 Confidentiality

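### C.3.e confines the baseline medical record and Adverse Events Log to the weight loss group while E.3 covers everyone, so control-arm events may be under-ascertained

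*Combined protocol and SAP*

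**What the plan says.** **The arm-specific rule.** The last paragraph of C.3.e (Informed consent process) reads: "Participants assigned to the weight loss group will notify the research study staff of any pre-existing medical conditions". It extends to injuries and recent operations at baseline and to medical problems arising during the programme. It then says: "Their responses at baseline and throughout the weight loss intervention will be recorded on an Adverse Events Log". Controls are not mentioned.

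**The rules without an arm restriction.**
- E.3 says that adverse events "will be collected as they occur, regardless of whether it is considered related to the weight loss intervention".
- E.3 adds that musculoskeletal injuries, and major medical events not documented before, "will be systematically collected on all participants during the study period using standardized forms from our prior work".
- E.3.c says: "The adverse event form will be used by study staff to report injuries or other adverse events reported by participants throughout the study".
- C.3.b deals with "potential participants who self-reported to have pre-existing health conditions". These people need medical clearance before enrollment, whichever arm they later join.

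**Contact and exposure.** The weight loss group has a weekly coaching call for 15 weeks (C.4.a). C.7 gives both arms a baseline and a 15-week visit. Table 3 lists no adverse event form at either visit. For controls, C.5 says: "Participants will be asked to meet the 2018 Physical Activity Guidelines for Americans". It describes no staff contact with them between the visits.

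**Use of the data.** D.1.a lists "Intervention-related adverse events, satisfactory, and other feasibility assessments" among the items to be assessed, and Aim 1 expects few such events. Table 5 provides for monthly review of adverse event rates, injuries included. No between-arm comparison of events is specified.

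**The concern.** Three things follow from reading these sections together.

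- **Conflict.** C.3.e and E.3 name different populations. Three instruments appear (the log, the standardized forms and the adverse event form), and nothing says how they relate. Site staff following C.3.e would do something different from staff following E.3.
- **No matching baseline for controls.** E.3 asks whether a major event was already documented. In a control participant that needs a baseline history, and C.3.e takes one only from people already assigned to the other arm. Screening asks about conditions that call for clearance; it is not stated to be a full history covering injuries and operations.
- **Unequal chance of detection.** A coach who speaks to a participant every week will hear about a sore knee. A control participant has to volunteer it or remember it at week 15. Inclusion criterion 3 selects people below the activity guidelines, and controls are asked to reach them, so they carry some exercise risk. E.1 itself acknowledges that starting a physical activity program raises risk.

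At stake are safety capture in the control arm, what the monthly review can see before week 15, and the soundness of any by-arm description of events carried forward to the larger trial.

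**Working it through.** The plan gives no figure on this point, so there is nothing to reproduce. The check compares the text, counts contacts and uses one identity.

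**1. Coverage, side by side.**
- Baseline conditions, injuries and operations: weight loss group only, after assignment (C.3.e).
- Conditions needing clearance: everyone, before enrollment (C.3.b).
- Later medical problems on the Adverse Events Log: weight loss group only (C.3.e).
- Injuries and major events on standardized forms: everyone (E.3), with no stated times of asking.
- Adverse event form: whatever participants report (E.3.c), with no stated times of asking.

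The first and third items are arm-specific. The fourth and fifth are not, but they give no occasion on which a control is asked.

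**2. Scheduled contacts at which an event could surface.**
- Weight loss arm: 15 calls + 2 visits = 17, of which 15 + 1 = 16 come after baseline.
- Control arm: 2 visits, of which 2 − 1 = 1 comes after baseline.

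Between the visits, capture in controls rests on the E.3 instruction that participants contact the principal investigator or their own provider.

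**3. Effect on a by-arm description.** Let both arms have the same true event risk p, with capture probabilities c_W (weight loss) and c_C (control). The expected recorded proportions are p × c_W and p × c_C, so

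apparent ratio = (p × c_W) / (p × c_C) = c_W / c_C.

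The true risk cancels. The documents give no capture rates, so these are assumptions, with c_W = 1:
- c_C = 1.00: 1 / 1.00 = 1.0
- c_C = 0.75: 1 / 0.75 = 1.33
- c_C = 0.50: 1 / 0.50 = 2.0

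In counts, taking an assumed 20% risk and the lowest capture: 30 × 0.20 = 6 of 30 (20%) against 20 × 0.20 × 0.50 = 2 of 20 (10%).

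**4. Effect on the Aim 1 safety result.** Intervention-related events are counted in the group receiving the intervention. That count depends on c_W and not on c_C, so missed control events leave it unchanged.

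**The case against.** The strongest reply is that E.3 is the dedicated adverse event section, that C.3.e is one paragraph about consent, and that nothing ranks C.3.e above E.3. On that view the trial collects events on everyone and C.3.e is loose drafting. The standardized forms from earlier work are not in the documents and may contain a schedule. Both arms attend at 15 weeks. Relatedness is judged case by case under E.3.b, from timing, known pattern and alternative cause, and not against a control-arm rate. No comparison of arms is planned.

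Much of this stands, and it rules out several stronger readings:
- A reader of C.3.e alone might infer that events are logged only in the coached arm. E.3 and E.3.c contradict that, and screening covers clearance-type conditions in everyone.
- A reader might infer that a planned safety comparison is invalid. The plan contains none.
- A reader might infer a two-fold false excess. That is one end of an assumed range which starts at no distortion.
- A reader might infer that controls are prescribed strength training. C.5 only makes a manual and videos available as examples of form; the request to meet the activity guidelines is the firm one.

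The reply does not remove the contradiction between the two sections, the absence of a specified full baseline history for controls, or the 16-to-1 difference in contacts after baseline. A general promise of systematic collection does not equalise ascertainment when one arm is spoken to weekly and no time of asking is stated for the other.

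**Conclusion.** The point holds in a limited form. C.3.e sets an arm-specific rule that conflicts with E.3, and the stated contact pattern makes under-ascertainment in controls likely enough to correct. If events are described by arm, the bias runs towards an apparent excess in the coached arm. Its size cannot be determined from the documents: the ratios of 1.0 to 2.0 assume equal true risk, full capture in the coached arm and control capture between 100% and 50%. The conclusion also assumes that the unseen forms do not already set common times of asking. The completion and acceptability outcomes and the coached-arm count of intervention-related events are not affected. This is a correction worth making for control-arm safety and for an unbiased description; it does not threaten the primary result.

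**What to change.** Reconcile C.3.e with E.3:
- Take the record of conditions, injuries and recent operations from all participants before allocation.
- Name one adverse event instrument for both arms, and say how the log, the standardized forms and the adverse event form relate to it.
- Add the same structured adverse event form for both arms at the existing 15-week visit, and list it in Table 3. Having participants complete it themselves, on paper or in REDCap, would help keep the assessors blinded as C.7 intends.
- Base any by-arm description on that common form, and state how many in each arm completed it. Report events volunteered on coaching calls separately.

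A short REDCap check at a fixed mid-point in both arms is optional. It would shorten recall, at the price of one extra contact in the control arm.

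The cost is revised wording and a few minutes per participant. One limitation remains: a single 15-week form relies on recall and misses people who do not attend, and D.1.b projects 20% attrition.

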alternative exercise options, and provide simple tips for proper exercise form. These videos have been successfully implemented to facilitate home-based exercise in prior lifestyle interventions led by the investigative team. Each week participants will gradually increase their exercise duration and intensity in increments of 10-30 min until attaining the target physical activity volume goal.

C.4.d Behavioral component

Each week, participants will receive a 30-45 minute telephone counseling session that provides behavioral change techniques tailored to rural populations using the contemporary principles of cultural-tailoring and Social Cognitive Theory (105), and focus on motivation, relapse prevention, emotional distress, time management, and overcoming barriers. Each session will include a review of the previous week's activity, planned weekly lessons, dietary and exercise goals for the subsequent week, and strategies tailored to each participant to improve self-efficacy, social support, and overcome barriers. Additionally, group messages following the weekly telephone counseling is integrated with the behavioral component to promote independent adherence to lifestyle modification.

Participants will also receive a physical activity tracker (e.g., Fitbit) and a weight scale. Participants will learn how to use the Fitbit and will wear it during the entire study period. Participants will learn how to conduct self-measurements and record body weight each week, as well as set up MyFitnessPal (or using paper log) to self-monitor dietary intake and physical activity throughout the 15-week study period.

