Objectively-determined minutes of PA participation will be assessed and The ActivPAL captures free-living sedentary and ambulatory PA and is well-established as one of the most accurate wearable activity monitors

(115). The monitor will be set to collect PA data using the manufacturer settings and is affixed to the midline of patients' right thigh in a waterproof pouch allowing for continuous wear time. Participants will be provided verbal and written instructions on how to wear the ActivPAL and wear the monitor 24 hours per day for the 7 consecutive days following the completion of the study assessment visits. In the event of wear time problems, patients must have at least 10 hours per day of wear time on 4 days of the week (including at least 1 weekend day) for a valid assessment. Monitors will be returned to trial staff via U.S. postal service.

Participants will also complete self-reported Leisure-Time Exercise Questionnaires (116) in the 1st and 15th week.

7. Dietary intake

All participants will complete 7-day food checklist for at the 1st and 15th week. This food checklist was developed by the National Cancer Institutes that comprised of a list of foods. Over the course of a day, participant makes a check beside a food each time she or he eats it. It yields estimates of macro nutrient intake, as well as intake by specific food groups. Participants in the weight loss intervention will also be encouraged to complete daily food log using MyFitnessPal (or paper log) during the trial. The food log and weekly summary of caloric and macronutrient intake will be regularly monitored by the trial's staff and registered dietitian to track adherence.

8. Self-Efficacy and Social Support

Participants will be asked to complete self-reported Healthy Weight and Eating Self-Efficacy, Multi-dimensional Self-Efficacy scales (117-119), as well as adapted Social Support Inventory for Physical Activity (SSPA) and Eating Habits (SSEH) questionnaires (120, 121).

9. Physical fitness

Participants will be asked to complete valid and reliable timed performance-related mobility tasks, such as 400-meter walk and lift and carry task (122-125). These assessments at baseline will serve as a reference to tailor exercise counseling for each participant.

C.9. Timeline

Table 4. Study Timeline

ACTIVITY	Year 1												Year 2											
	1	2	3	4	5	6	7	8	9	10	11	12	1	2	3	4	5	6	7	8	9	10	11	12
Database Development and Training	→																							

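### The diet and activity baseline is timed to the first week and to the days after the visit, and nothing requires it to be finished before allocation is known or treatment begins

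*Combined protocol and SAP*

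**What the plan says.** Three baseline measures are not timed by the visit alone.

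- **Food checklist (C.7.b item 7):** "All participants will complete 7-day food checklist for at the 1st and 15th week".
- **Exercise questionnaire (C.7.b item 6):** "Participants will also complete self-reported Leisure-Time Exercise Questionnaires (116) in the 1st and 15th week".
- **ActivPAL (C.7.b item 6):** participants are to "wear the monitor 24 hours per day for the 7 consecutive days following the completion of the study assessment visits".

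The opening of C.7 gives a different frame: in-person outcome assessments at baseline and again 15 weeks later, by staff blinded to allocation. C.6 adds that self-report measures are to be done remotely or by mail, so the visit date does not fix when they are filled in.

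The other numbered weeks are those of the intervention. Table 2 starts at Week 1 with a 30-60 minute exercise goal. C.4.d has the coached arm "self-monitor dietary intake and physical activity throughout the 15-week study period".

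Both arms receive something early. E.2 gives the coached arm a Fitbit when the study begins. C.5 gives controls their brochures at the same point and asks them to meet activity guidelines and change their diet.

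On order of events, C.3.d forms a wave once 6-12 people have consented and enrolled. C.3.e puts consent before the baseline assessment. It also says "Participants assigned to the weight loss group will notify the research study staff of any pre-existing medical conditions", and that this happens "at baseline before they start the weight loss intervention".

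**The concern.** A baseline for a behavioural outcome should describe behaviour before the participant knows the allocation and before anyone asks for change. Here the two seven-day records are tied to a first week that shares its numbering with the intervention, or to the days after a visit. If either overlaps the start of treatment, the recorded baseline already contains part of the response.

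D.1.b plans between-arm comparisons of change in physical activity and dietary intake, to supply effect sizes for a larger trial. Assessor blinding does not help, because the participants produce these records and will know whether they receive coaching calls or a brochure.

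**Working it through.** The plan states no figure on this point, so there is none to reproduce. The check sets the timing rules side by side and counts days.

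**1. Is there a built-in gap?** Two visits 15 weeks apart span 15 × 7 = 105 days. Fifteen full intervention weeks also span 105 days. If all of them lie between the visits, the gap is 105 − 105 = 0 days. Counting only from the first to the fifteenth weekly call, 14 × 7 = 98 days, up to 7 days could be absorbed, but the plan does not say that it counts this way.

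**2. Does any rule order these recordings against treatment?**

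| Rule | What it covers |
|---|---|
| Consent before baseline assessment (C.3.e) | Consent only |
| Conditions reported before the intervention (C.3.e) | Medical history, coached arm only |
| Baseline fitness tests used to tailor counselling (C.7.b item 9) | Fitness tests only |
| Wave formed on consent and enrolment (C.3.d) | No condition that baseline records are complete |

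None covers the checklist, the questionnaire or the monitor week.

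**3. How many baseline days could fall after the start?** Let L be the full days from the baseline visit to the first treatment element (brochure, Fitbit or first call).

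- Checklist, if the first week is intervention week 1: 7 of 7 days, whatever L is.
- ActivPAL (and the checklist, if its first week means the week after the visit): days after the start = max(0, 7 − L), and days before it = min(7, L).

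The last column below applies the plan's own validity rule (10 hours of wear on 4 days, at least one of them a weekend day) to the pre-start days alone. It assumes that each such day has enough wear, and counts how many of the 7 possible starting weekdays pass.

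| L | Pre-start days | Days after start | Starting weekdays passing |
|---|---|---|---|
| 0 | 0 | 7 | 0 of 7 |
| 3 | 3 | 4 | 0 of 7 |
| 4 | 4 | 3 | 5 of 7 (Mon-Thu and Tue-Fri fail) |
| 5 | 5 | 2 | 6 of 7 (Mon-Fri fails) |
| 6 | 6 | 1 | 7 of 7 |
| 7 | 7 | 0 | 7 of 7 |

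**4. Which way would it bias the comparison?** For an analysis adjusted for baseline with slope β, bias = −β × (first-week shift in coached arm − first-week shift in control arm). A simple change score has β = 1. The documents give neither β nor the shifts. As an illustration only, assume shifts of 0-60 min/week in each arm (60 is the top of the Week 1 goal in Table 2; using it for controls is an assumption) and β of 0.3 to 0.8. The extreme at β = 0.8 is 0.8 × 60 = 48, so the bias lies between −48 and +48 min/week. It is zero if both arms shift equally. The sign is therefore undetermined.

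**The case against.** The strongest reply is that C.7 governs. It says baseline, Table 3 lists these instruments under that scheme, and the first and fifteenth weeks may be shorthand for the two assessment points. Table 2 numbers weeks for the coached arm only, whereas the checklist applies to everyone. Waves of 6-12 people at 4-5 per month take 6/5 = 1.2 to 12/4 = 3.0 months to fill, and C.9 starts recruitment in month 3 but intervention data collection in month 4. If the baseline visit precedes that wait, most participants would have no overlap.

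This stands as a reason for caution about what will happen. It does not close the gap: neither the waves nor the calendar sets a minimum per participant, and the plan does not say whether the visit comes before or after the wait.

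Several stronger inferences are tempting but not supported.

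- **That the baseline will be recorded after disclosure.** The text permits this but does not establish it. The C.3.e sentence about people assigned to the weight loss group may simply name the group concerned.
- **That both arms will already have been asked to change.** Controls are asked through C.5. For the coached arm, a Fitbit is not itself a request. The requests come with the calls, and the first call is not dated.
- **That the questionnaire is compromised in the same way.** It takes 5 minutes and no recall period is stated. If it asks about a usual or previous week, completing it in week 1 could still describe earlier behaviour.
- **That last value carried forward shows the scale of this problem.** At 20% attrition, 6 of 30 coached and 3-4 of 15-20 control participants would have their baseline carried forward, but that count is the same whenever the baseline is taken.

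**Conclusion.** The point holds as a missing safeguard with two timings that need reconciling. Followed literally, C.7.b puts the seven-day checklist and monitor baseline in the first intervention week. On that reading 7 of 7 checklist days come after the start, and max(0, 7 − L) monitor days do. A benign reading is available but is not written down. The absence of an ordering rule is established for the text available for review, from which some pages had been removed.

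The reach is limited to the exploratory diet and activity change comparisons in D.1.b. The feasibility outcome is unaffected, as are weight, body composition, lipids and inflammatory markers, which are measured at the visit. No size or direction of bias can be given. This is a cheap improvement to a pilot, worth making because these comparisons are meant to inform the next trial.

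**What to change.** Reconcile the first week in C.7.b with baseline in C.7, and state when the 15-week clock starts. Then require that the baseline seven-day ActivPAL wear, seven-day food checklist and exercise questionnaire be completed after consent and before allocation is disclosed, materials are given or the first call is made. State the questionnaire's recall period.

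If a monitor week still overlaps the start, use only pre-start days, provided that they meet the existing four-day and weekend-day rule. Otherwise treat that baseline as missing, and say how such participants enter the comparison.

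**Cost.** The delay before the first call is up to about one week per participant, and possibly none for those already waiting for a wave. No new instrument or staff is needed. If all 15 weeks follow the baseline week, the visits are up to 7 + 105 = 112 days (16 weeks) apart, so the spacing in C.7 needs rewording. One week of accrual is 7/30.44 × 4 = 0.92 to 7/30.44 × 5 = 1.15 participants. Recruitment from month 3 of Year 1 through month 7 of Year 2 is 10 + 7 = 17 months, which at 4-5 per month gives 68-85 against a cap of 50. The effect on the enrolment target should therefore be little or none.
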